## **11. Statistical Analyses:**

EEG data will be analyzed using an established Matlab toolbox, CENA (The Chicago Electrical Neuroimaging Analytics). Standard statistical analyses will be performed using SPSS. Compared to fMRI, which has a very low temporal resolution, high-density EEG/ERP has a very high temporal resolution ([name] & Bianchi-Demicheli, 2008). When combined with brain source localization algorithms, high-density EEG-ERP is called electrical neuroimaging. Electrical neuroimaging can identify dynamical patterns of communication between brain regions that contrast analyses, such as fMRI, may not detect. This proposal takes advantage of electrical neuroimaging and a new suite of tools (i.e., the Chicago Electrical Neuroimaging Analytics, CENA), that [name] developed and validated recently for segmenting high-density electrical brain activity (Cacioppo et al., 2014, 2015). Compared to the standard waveform analysis of event-related potentials (ERP) components that provide local information about amplitude and latency of the brain electric signal collected from one electrode in response to a stimulus, CENA provides general information about the stable momentary configuration of the global scalp electric potential over a high-density multi-channel electrode array. This approach provides information about the temporal sequence of discrete information processing operations evoked by the presentation of a stimulus within the context of a particular experimental task. That temporal sequence of information processing includes a series of stable brain microstates, each of which is characterized by specific cognitive computations and a relatively stable spatial distribution of brain activity. Combined with brain source localization algorithms, this method can then provide a video-clip of the potential brain sources that sustain every electrical brain state recorded from the surface of the scalp –without having to perform an fMRI scan (see attached example). The brain microstate approach complements the traditional approach of ERP peaks and troughs at specific electrode positions, but with more comprehensive analyses of time-varying activity across the entire scalp (Cacioppo et al., 2014, 2015).

Subjects who do not adhere to the recommended dosing regimen will not be discontinued from the study. Rather, data from these subjects should be included in an intent-to-treat analysis.

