and mechanism of missing data. A 2 (Treatment Type: Addyi or Placebo) x 2 (Group Type: pre- or post-menopausal) X 2 (type of stimuli: desired, nondesired) x 3 time (Visit 1, Visit 2, Visit 3) repeated-measures ANOVA will be performed on the reaction times and ratings to assess for main effects and interaction effects. P values, confidence interval, and effect sizes will be reported.

iii. Eye-tracking Data: A similar ANOVA will be performed for the following dependent variables: onset to first fixation and duration of fixation. As in our 2014's paper (Bolmont, Cacioppo, & Cacioppo), we will also analyzed include the subjects' visual area of interest (face vs. body) as a within-subject factors in our ANOVA.

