iii. Electrophysiological Data: EEG data will be analyzed using an established Matlab toolbox, CENA (The Chicago Electrical Neuroimaging Analytics). Standard statistical analyses will be performed using SPSS. Compared to fMRI, which has a very low temporal resolution, high-density EEG/ERP has a very high temporal resolution ([name] & Bianchi-Demicheli, 2008). When combined with brain source localization algorithms, high-density EEG-ERP is called electrical neuroimaging. Electrical neuroimaging can identify dynamical patterns of communication between brain regions that contrast analyses, such as fMRI, may not detect. This proposal takes advantage of electrical neuroimaging and a new suite of tools (i.e., the Chicago Electrical Neuroimaging Analytics, CENA), that [name] developed and validated recently for segmenting high-density electrical brain activity (Cacioppo et al., 2014, 2015). Compared to the standard waveform analysis of event-related potentials (ERP) components that provide local information about amplitude and latency of the brain electric signal collected from one electrode in response to a stimulus, CENA provides general information about the stable momentary configuration of the global scalp electric potential over a high-density multi-channel electrode array. This approach provides information about the temporal sequence of discrete information processing operations evoked by the presentation of a stimulus within the context of a particular experimental task. That temporal sequence of information processing includes a series of stable brain microstates, each of which is characterized by specific cognitive computations and a relatively stable spatial distribution of brain activity. Combined with brain source localization algorithms, this method can then provide a video-clip of the

potential brain sources that sustain every electrical brain state recorded from the surface of the scalp –without having to perform an fMRI scan (see attached example). The brain microstate approach complements the traditional approach of ERP peaks and troughs at specific electrode positions, but with more comprehensive analyses of time-varying activity across the entire scalp (Cacioppo et al., 2014, 2015).

A significant and clinically meaningful change from baseline for each subject pre- and post-treatment with flibanserin is as follows:

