### **Adverse Reactions Leading to Discontinuation**

The discontinuation rate due to adverse reactions was 13% among patients treated with 100 mg ADDYI at bedtime and 6% among patients treated with placebo. Table 1 displays the most common adverse reactions leading to discontinuation in four trials of premenopausal women with HSDD.

**Table 1: Adverse Reactions\* Leading to Discontinuation in Randomized, Double-blind, Placebo-controlled Trials in Premenopausal Women with HSDD**

	PLACEBO (N=1556)	ADDYI (N=1543)
Dizziness	0.1%	1.7%
Nausea	0.1%	1.2%
Insomnia	0.2%	1.1%
Somnolence	0.3%	1.1%
Anxiety	0.3%	1%

\*Adverse reactions leading to discontinuation of > 1% of patients receiving 100 mg ADDYI at bedtime and at a higher incidence than placebo-treated patients.

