**13. Monitoring of Safety:**

A researcher will be present with participants during the duration of the experiment. While participants are in a separate room sheltered from electrical interference for EEG recording, researchers will monitor participants' well-being via cameras and microphones within this room. Participants will have the ability to communicate with researchers through these microphones and may opt out of participation at any time. Participants will also be provided with the IRB's contact information on the consent form, and we will contact IRB should any adverse effects occur.

Participants will be advised not to drive, operate machinery, or do things that require clear thinking until at least 6 hours after taking flibanserin and until they know how flibanserin affects them. This has been addressed in the informed consent and will be discussed with participants.

Regarding Addyi's side effects: Subjects will be directed to call a member of the study team if they believe they are experiencing any side effects.

Vital signs (blood pressure, pulse, respiratory rate, temperature, height, weight) will be obtained at every visit. Orthostatic vital signs will be used in terms of blood pressure and pulse.

No baseline laboratory testing will be done.

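### The only treatment-by-time model written out is a three-visit repeated-measures ANOVA, which in its usual form drops women who miss one visit, even if measured at week 8, despite a promised intent-to-treat analysis.

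*Combined protocol and SAP*

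**What the plan says.** Section 11 (Statistical Analyses) sets the retention rule: "Subjects who do not adhere to the recommended dosing regimen will not be discontinued from the study", and "data from these subjects should be included in an intent-to-treat analysis". The rule concerns dosing. It does not mention missed visits, and no intent-to-treat set is defined.

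Under Statistical Hypotheses, the behavioural model crosses treatment, menopausal group, stimulus type and time: "x 3 time (Visit 1, Visit 2, Visit 3) repeated-measures ANOVA will be performed on the reaction times and ratings". For eye tracking, "A similar ANOVA will be performed for the following dependent variables: onset to first fixation and duration of fixation", with area of interest (face or body) as a further within-subject factor. SPSS is the named software. For EEG, the primary outcome, the plan names the CENA toolbox and adds only that "Standard statistical analyses will be performed using SPSS"; it gives no treatment-by-time model.

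Section 4 defines the primary outcome, and the list after it the secondary outcomes including eye tracking, as change from baseline at 8 weeks. Section 5 calls the 4-week visit mid-term. The pattern and mechanism of missing behavioural data will be examined, but no handling rule follows. The text available for review jumps from Section 6 to Section 8 and from Section 18 to Section 20, so a rule in Sections 7 or 19 cannot be excluded.

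**The concern.** A conventional repeated-measures ANOVA takes one row per woman and needs a value in every within-subject cell. Here that is 2 stimuli x 3 visits = 6 cells, and more for eye tracking. A woman who misses week 4 and returns at week 8 is dropped, although her baseline and week-8 values give the 8-week change directly. The documents do not state this deletion; it is a property of the usual procedure, and nothing in the plan overrides it.

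Two things are at stake. Measured data are discarded, which costs precision. And if women who stop tablets miss visits more often than others, the analysed sample tilts towards women who tolerated the drug, yet the result would be labelled intent to treat. Section 12 gives a reason to expect unequal stopping: "The discontinuation rate due to adverse reactions was 13% among patients treated with 100 mg ADDYI at bedtime and 6% among patients treated with placebo". It adds that most of the common reactions began within 14 days, which is before the week-4 visit.

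**Working it through.** **1. The plan's own figure.** Section 10 states 95% power at N = 120, alpha 0.05 and effect size 0.14 for a within-between interaction in repeated-measures ANOVA. The number of groups k, the number of measurements m and the correlation rho are not given. Taking k = 4, m = 6, rho = 0.5 and the effect size as Cohen's f:

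- lambda = f² x N x m / (1 - rho) = 0.0196 x 120 x 6 / 0.5 = 28.2
- df = (k - 1)(m - 1) = 15 and (N - k)(m - 1) = 580
- power = 0.948

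So the 95% reproduces on this reading when all 120 women supply all six cells. On the same inputs, power is 0.934 with 114 complete women, 0.917 with 108 and 0.877 with 97. Other readings also come near 95% (k = 2, m = 6, rho = 0.3 gives 0.952), so these values are illustrative.

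**2. Measured women lost to a missed visit.** Assume an independent chance q of missing each of Visits 2 and 3. Complete rows = 120(1 - q)²; week-8 values = 120(1 - q); deleted although measured at week 8 = 120q(1 - q).

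| q | Complete rows | Week-8 values | Deleted |
|---|---|---|---|
| 5% | 108.3 | 114 | 5.7 |
| 10% | 97.2 | 108 | 10.8 |
| 15% | 86.7 | 102 | 15.3 |

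In a constructed data set of 120 women with 12 missing Visit 2 only, complete rows fell to 108. A mixed model used all 120 women (348 observations).

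**3. Direction and size of bias.** Assumptions:

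- 60 women per arm
- effect 0.48 SD while on tablets and zero after stopping
- stopping 13% against 6%
- women who stay on tablets attend each follow-up visit with probability 0.95

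The true intent-to-treat effect is 0.48 x 0.87 = 0.418. Let a and s be the probabilities that an adherer and a stopper enter the analysed sample. Then

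estimate = 0.48 x 0.87a / (0.87a + 0.13s).

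For the three-visit sample, a = 0.95² = 0.9025 and s is the product of the stopper's two attendance probabilities. For everyone with a week-8 value, a = 0.95 and s is her Visit 3 probability. Expected stoppers: 60 x 0.13 + 60 x 0.06 = 11.4. Deleted although measured at week 8 = 108.6 x 0.95 x 0.05 + 11.4 x P(attend Visit 3) x P(miss Visit 2).

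| Stoppers' attendance, Visit 2 / Visit 3 | Three-visit sample | All with week 8 | Deleted |
|---|---|---|---|
| 95% / 95% (like others) | 0.418 | 0.418 | 5.7 |
| 90% / 90% | 0.423 | 0.420 | 6.2 |
| 80% / 80% | 0.434 | 0.426 | 7.0 |
| 50% / 80% | 0.450 | 0.426 | 9.7 |
| 0% / 95% | 0.480 | 0.418 | 16.0 |
| 0% / 0% | 0.480 | 0.480 | 5.2 |

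Example, 50% / 80%: s = 0.40, so 0.48 x 0.7852 / (0.7852 + 0.052) = 0.450. Simulations with 4,000 replicates agree within simulation error (0.436 against 0.429 for 80% / 80%; 0.454 against 0.429 for 50% / 80%).

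**4. Precision.** With correlation 0.5 between visits, the change has variance 2(1 - 0.5) = 1. At 5% random loss alone the SE is √(2/54.15) = 0.192 for complete rows against √(2/57) = 0.187 for all with week 8. In the 0% / 95% row it is about 0.20 against 0.19.

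**The case against.** The strongest reply is that the retention rule is about tablets, and Section 24 measures adherence by pill count. A woman who stops tablets but attends Visits 1 to 3 stays in the ANOVA. A reader might infer that the rule has no effect because the model removes the women it was written for. That does not hold: deletion follows from a missed visit, and in the 50% / 80% row about 11.4 x 0.40 = 4.6 of the 11.4 stoppers remain in the analysis.

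Other objections also stand:

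- The ANOVA is specified for reaction times, ratings and eye tracking. The documents do not say that the primary EEG outcome will be analysed this way, and questionnaire change scores need only Visits 1 and 3.
- The 13% and 6% come from 24-week trials in premenopausal women. This trial lasts 8 weeks and half its planned sample is postmenopausal, so those rates illustrate and do not predict.
- In moderate patterns the gap between the two samples is at most 0.024 SD, against an SE of about 0.19. The comparison using all week-8 values is itself slightly high there.
- If stoppers miss both follow-up visits, changing the model recovers little.

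None of this supplies a missed-visit rule. Examining the pattern of missing data diagnoses the problem but does not bring deleted women back.

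**Conclusion.** The concern holds in limited form. The plan promises intent to treat but writes out a model that, run conventionally, discards women measured at baseline and week 8 because week 4 is missing. The sure cost is data and a little precision: about 6 women at 5% random loss per visit, 11 at 10% and 15 at 15%.

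Bias is conditional. It is nil if stoppers attend like the others, and small in moderate patterns (0.43 to 0.45 against 0.43, true value 0.42). A reader might infer an overstatement of about 15% (0.480 / 0.418 = 1.15). That needs every stopper to skip Visit 2 and then return for Visit 3 as reliably as everyone else, and the documents give no ground to expect it. All these sizes rest on assumed attendance, zero effect after stopping and stopping rates borrowed from longer trials. The change should be made because it costs little and makes the analysis match the promise, not because a large bias has been shown.

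**What to change.** In Section 11, under behavioural and eye-tracking data, replace the three-visit repeated-measures ANOVA with a likelihood-based mixed model with the same factors (MIXED in SPSS). Fit it by assigned arm to all available visits of every randomised woman, and name the treatment difference in change from baseline to week 8 as the target contrast. State the missing-at-random assumption that the model makes. Use the same approach for the EEG summary measures, so that the primary outcome also has a named treatment-by-time model.

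Beside the intent-to-treat sentence, add that women who stop tablets are still asked to attend the already scheduled Visits 2 and 3. This matters because the model alone cannot recover women who miss both.

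Cost: revised wording, slightly more analysis work and some effort to keep stoppers attending; no added visits, participants or measurements. The reported effect may be slightly smaller than in women who attend everything.

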**Statistical Hypotheses:**

a. The research questions of this double-blind randomized study are: (a) to determine the pre-post change in the Flibanserin group vs. Placebo group in women with hypoactive sexual desire disorder (HSDD), (b) to compare the effect is Flibanserin (vs. placebo) on behavioral and brain changes between pre-menopausal women and postmenopausal women, (c) to investigate the extent to which post-Flibanserin's regional brain activations (compared to pre-Flibanserin's regional brain activations) are associated with changes in symptoms and behavior (as measured with self-report measures of sexual desire and/or eye-tracking movements), and (d) to investigate the extent to which Flibanserin normalizes brain activity in women with HSDD compared to matched healthy controls. The statistical hypotheses include the following:

i. Demographics: Statistical analyses for demographic and self-report measures will be computed using SPSS software. Prior to inferential analyses, descriptive statistics, including distributions, means, standard deviations, skewness, and kurtosis will be generated. Data will also be examined for the pattern and mechanism of missing data. Continuous data will be tested for normality and homogeneity of variance. Potential differences between the treatment and placebo groups in terms of demographic and behavioral measures will be explored using multivariate analysis of variance (MANOVA) or appropriate non-parametric tests as appropriate. Similar analyses will be performed to detect potential differences between the pre-menopausal subjects and the post-menopausal subjects. The overall significance level for these analyses will be at 5%, and effect sizes and confidence intervals will also be performed to test hypotheses about correlations.

ii. Behavioral data: Statistical analyses will be computed using SPSS software. Reaction times and performance data (ratings) will be screened. Prior to inferential analyses, descriptive statistics, including distributions, means, standard deviations, skewness, and kurtosis will be generated. Data will also be examined for the pattern

and mechanism of missing data. A 2 (Treatment Type: Addyi or Placebo) x 2 (Group Type: pre- or post-menopausal) X 2 (type of stimuli: desired, nondesired) x 3 time (Visit 1, Visit 2, Visit 3) repeated-measures ANOVA will be performed on the reaction times and ratings to assess for main effects and interaction effects. P values, confidence interval, and effect sizes will be reported.

iii. Eye-tracking Data: A similar ANOVA will be performed for the following dependent variables: onset to first fixation and duration of fixation. As in our 2014's paper (Bolmont, Cacioppo, & Cacioppo), we will also analyzed include the subjects' visual area of interest (face vs. body) as a within-subject factors in our ANOVA.

iii. Electrophysiological Data: EEG data will be analyzed using an established Matlab toolbox, CENA (The Chicago Electrical Neuroimaging Analytics). Standard statistical analyses will be performed using SPSS. Compared to fMRI, which has a very low temporal resolution, high-density EEG/ERP has a very high temporal resolution ([name] & Bianchi-Demicheli, 2008). When combined with brain source localization algorithms, high-density EEG-ERP is called electrical neuroimaging. Electrical neuroimaging can identify dynamical patterns of communication between brain regions that contrast analyses, such as fMRI, may not detect. This proposal takes advantage of electrical neuroimaging and a new suite of tools (i.e., the Chicago Electrical Neuroimaging Analytics, CENA), that [name] developed and validated recently for segmenting high-density electrical brain activity (Cacioppo et al., 2014, 2015). Compared to the standard waveform analysis of event-related potentials (ERP) components that provide local information about amplitude and latency of the brain electric signal collected from one electrode in response to a stimulus, CENA provides general information about the stable momentary configuration of the global scalp electric potential over a high-density multi-channel electrode array. This approach provides information about the temporal sequence of discrete information processing operations evoked by the presentation of a stimulus within the context of a particular experimental task. That temporal sequence of information processing includes a series of stable brain microstates, each of which is characterized by specific cognitive computations and a relatively stable spatial distribution of brain activity. Combined with brain source localization algorithms, this method can then provide a video-clip of the

potential brain sources that sustain every electrical brain state recorded from the surface of the scalp –without having to perform an fMRI scan (see attached example). The brain microstate approach complements the traditional approach of ERP peaks and troughs at specific electrode positions, but with more comprehensive analyses of time-varying activity across the entire scalp (Cacioppo et al., 2014, 2015).

A significant and clinically meaningful change from baseline for each subject pre- and post-treatment with flibanserin is as follows:

Median effective doses of flibanserin on increase in SD level will demonstrate at least a medium effect size (e.g., Cohen's  $d > 0.48$ ) relative to placebo (PBO); and at least a medium effect size (Cohen's  $d > 0.48$ ) between flibanserin and PBO conditions in SD levels; and relationship between change in SD self-report levels and change in behavioral responses (reaction times) during SD paradigm in flibanserin (vs PBO) is of at least a medium effect size ( $r > 0.48$ ); or relationship between change in flibanserin and change in electrophysiological responses during SD paradigms in flibanserin (vs. PBO) is of at least a medium effect size ( $r > 0.48$ ); Relationship between change in Flibanserin and change in eye movement responses during SD paradigms in Flibanserin(vs. PBO) is of at least a medium effect size ( $r > 0.48$ ). There will be no adverse events of more than mild severity which are rated as possibly, probably, or definitely related to acute, oral administration of flibanserin to a greater extent than PBO in HSDD participants.

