### **Secondary Outcome Measures:**

- Eye movement tracking: movements to first saccades. We will be analyzing change from baseline eye movement tracking results at 8 weeks.
- Female Sexual Function Index: change from baseline to final score at 8 weeks.
- UCLA Loneliness Scale: change from baseline to final score at 8 weeks.
- Life Satisfaction Scale: change from baseline to final score at 8 weeks.
- Body Dysmorphic Disorder Questionnaire: change in answers from baseline to final visit at 8 weeks.
- Hamilton Anxiety and Depression Scale: change from baseline to final score at 8 weeks.
- Rosenberg Self-Esteem Scale: change from baseline to final score at 8 weeks.
- Hostility Measure: change from baseline to final score at 8 weeks.
- Female Sexual Distress Scale-Revised: change from baseline to final score at 8 weeks.
- IOS Scale with Partner: change in answers from baseline to final answers at 8 weeks.
- Body image measure: change in baseline to final score at 8 weeks.
- Sexual Desire Inventory: change in baseline to final score at 8 weeks.
- Marital Satisfaction Scale: change in baseline to final score at 8 weeks.

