## **10. Type and Number of Experimental Subjects:**

We expect to collect data from a total of 120 subjects between the age of 21 and 74 years. We will be testing premenopausal and postmenopausal women with hypoactive sexual desire disorder. Flibanserin is FDA approved for premenopausal but not postmenopausal women with HSDD. Women who are pregnant (or think they are pregnant), or who are nursing (or breastfeeding), or women who report not being able to stop drinking alcohol during the duration of the study will NOT be tested.

**Power:** Using G\* power calculation software (Version 3.1.9.2) for a within-between interaction in repeated measures ANOVA, a total sample size of 120 will yield 95% power to detect a significance, with alpha = .05 and an effect size of 0.14.

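### The ANOVA for reaction times, ratings and eye tracking is valid but neither adjusts for Visit 1 nor names a week-8 flibanserin-placebo contrast; doing both is a cheap, minor gain in precision

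*Combined protocol and SAP*

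**What the plan says.** Under Statistical Hypotheses in section 11, item ii plans a model with treatment (2), menopausal group (2), stimulus type (2) and visit (3): a "repeated-measures ANOVA will be performed on the reaction times and ratings to assess for main effects and interaction effects". For eye tracking, "A similar ANOVA will be performed for the following dependent variables: onset to first fixation and duration of fixation", with face or body added as a further within-woman factor. Visit 1, recorded before study drug, is one of the three levels of time. It is not a covariate anywhere in the plan.

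Other sections describe the comparison of interest:

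- Section 3 frames both aims around 8 weeks of flibanserin against placebo, the second by menopausal status.
- Secondary Outcome Measures says of eye tracking: "We will be analyzing change from baseline eye movement tracking results at 8 weeks".
- Research question (a) is "to determine the pre-post change in the Flibanserin group vs. Placebo group". Question (b) compares the flibanserin effect "on behavioral and brain changes between pre-menopausal women and postmenopausal women".
- Section 10 powers the trial "for a within-between interaction in repeated measures ANOVA".

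Item ii does not turn these into a named test. On missing visits it says "Data will also be examined for the pattern" and mechanism of missingness, but gives no handling. Section 11 also says of non-adherent women that "data from these subjects should be included in an intent-to-treat analysis".

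**The concern.** Two choices are left open. First, the pre-drug value is collected on every outcome but is not used for adjustment. In the treatment-by-time interaction it acts as a plain subtraction, which is less precise than regression on the baseline whenever the visits are imperfectly correlated.

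Second, a four-factor ANOVA produces 2^4 - 1 = 15 main effects and interactions per behavioural outcome, and the five-factor eye-tracking version 2^5 - 1 = 31. The plan does not say which of these answers question (a) or (b). They are not equally suitable. The treatment main effect, for example, averages in Visit 1, where no drug effect can exist.

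What is at stake is precision and a clear link between question and test, not validity.

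**Working it through.** **1. The plan's own figure.** Section 10 gives N = 120, f = 0.14, alpha 0.05 and power 95%. It does not state the correlation, the number of groups or the number of measurements. Take noncentrality = f^2 x N x m / (1 - rho), with df (k - 1)(m - 1) and (N - k)(m - 1). With k = 4 groups, m = 6 measurements (2 stimuli x 3 visits), and assumed rho = 0.5 and sphericity, noncentrality = 0.0196 x 120 x 6 / 0.5 = 28.2 on 15 and 580 df, and power is 0.948. The stated 95% is therefore reproducible, though other settings also come close (k = 2, m = 4 gives 0.965). It is the power of an omnibus interaction, not of a week-8 contrast.

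**2. Inputs for the comparison.** There are 60 women per arm (section 5). The week-8 difference is d = 0.48, which section 11 gives for sexual desire level; its use for these outcomes is an assumption. Data are complete and alpha is two-sided 0.05. Correlation rho between visits is not in the documents, so 0.3, 0.5 and 0.7 are shown, taken as equal for all pairs of visits. SD and rho are those of the response tested. If that response is the desired-minus-nondesired difference, the matching planned test is treatment-by-stimulus-by-time, which also has 2 df.

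**3. Planned 2-df test.** Noncentrality = (N/4) x SS / (1 - rho), on 2 and 232 df, where SS is the sum of squared deviations of the three visit differences from their mean.

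- Full by week 4 (0, 0.48, 0.48) or only at week 8 (0, 0, 0.48): SS = 0.1536. At rho 0.5, noncentrality = 30 x 0.1536 / 0.5 = 9.22.
- Linear build-up (0, 0.24, 0.48): SS = 0.1152. At rho 0.5, noncentrality = 6.91.

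**4. Baseline-adjusted week-8 contrast.** Variance per woman is 1 - rho^2. At rho 0.5, noncentrality = 0.48 / sqrt(2 x 0.75 / 60) = 3.04 (noncentral t).

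| rho | Planned: full by week 4, or only at week 8 | Planned: linear | Adjusted week 8 |
|---|---|---|---|
| 0.3 | 0.621 | 0.493 | 0.780 |
| 0.5 | 0.775 | 0.643 | 0.853 |
| 0.7 | 0.946 | 0.865 | 0.955 |
| 0.8 | 0.993 | 0.967 | 0.991 |

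**5. Against unadjusted week-8 change.** The variance ratio is (1 - rho^2) / [2(1 - rho)] = (1 + rho)/2, that is 0.65, 0.75 and 0.85 at rho 0.3, 0.5 and 0.7. It is below 1 for every rho below 1. Unadjusted change has power 0.596, 0.741 and 0.920.

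**6. Adverse case.** Suppose the effect is 0.48 SD at week 4 and 0.36 SD at week 8. Then SS = 0.1248, and at rho 0.5 the planned test has noncentrality 7.49 and power 0.681. The adjusted week-8 test has noncentrality 0.36 / sqrt(2 x 0.75 / 60) = 2.28 and power 0.617. At rho 0.7 the figures are 0.89 and 0.78; at rho 0.3 the two are about equal (0.53 and 0.54).

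**The case against.** The planned ANOVA does use Visit 1: treatment-by-time is a comparison of changes. The target is also partly stated already, through Aims 1 and 2, the eye-tracking outcome, questions (a) and (b) and the power statement, so the gap in the text is small. The effect size is borrowed from another outcome and no correlation is given, so the size of the benefit is uncertain. A single week-8 test can lose to the omnibus test. All of this stands, and it limits the point to a minor one.

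Several stronger readings are tempting and are not supported:

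- **That the ANOVA is invalid or the 95% power wrong.** Treating baseline as a response is legitimate, and step 1 reproduces the figure under plausible settings.
- **That the full gain over change scores is the gain over the plan.** The plan specifies a three-visit ANOVA, so the 2-df test is the fair comparator, and the gain over it is usually smaller.
- **That missing visits are a large part of the problem.** A standard repeated-measures ANOVA drops a woman who missed only Visit 2. But with an assumed 12% incomplete and rho 0.5, keeping such women moves the power of a change-score analysis only from 0.685 to 0.705.
- **That stimuli are sorted by the woman's own answer at each visit, making that factor depend on treatment.** Section 1 describes the task as asking for her judgement at that moment, but nothing in the plan says trials are classified that way for analysis.

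**Conclusion.** The point holds as a minor efficiency improvement. The plan leaves a recorded baseline unused for adjustment and does not name the contrast that its own aims call for. With d = 0.48, 60 per arm and complete data, adjustment raises power over the planned 2-df test by 0.16 to 0.29 at rho 0.3, by 0.08 to 0.21 at 0.5 and by 0.01 to 0.09 at 0.7. The lower figure applies if the effect is full by week 4 or appears only at week 8, the higher if it builds linearly. There is no gain at 0.8 if the effect is full by week 4, and there can be a loss if the effect is larger at week 4 than at week 8. Only the advantage over unadjusted week-8 change holds at every correlation below 1.

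The scope is eye tracking, a listed secondary outcome, and reaction times and ratings, which are on neither outcome list. A reader might extend the point to the primary EEG outcome. These items do not govern it, so it is not affected.

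**What to change.** Add to items ii and iii of Statistical Hypotheses:

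- For each outcome, compute the desired-minus-nondesired difference per woman and visit; for eye tracking, do so separately for face and body.
- Principal test: the flibanserin-minus-placebo difference at Visit 3, from an ANCOVA on the Visit 1 value and menopausal group. Include all randomised women with Visits 1 and 3, in their assigned arm, whether or not they attended Visit 2.
- Aim 2: the difference in that contrast between menopausal groups, from the treatment-by-menopausal-group term, with its 95% confidence interval.
- Keep the planned ANOVA (2x2x2x3, with face/body added for eye tracking) as a supporting analysis. It covers an effect that is larger at week 4.

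The cost is a few sentences and a standard procedure in SPSS, which the plan already uses. No new data, visits or women are needed. The downsides to state are the possible loss of power if the effect peaks at week 4, and reliance on a missing-at-random assumption for women without Visit 3.
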